### **8.1 Normality Testing**

The Shapiro-Wilk test and visual inspection of Q-Q plots were used to assess normality of continuous variables. Descriptive statistics are presented as mean  $\pm$  standard deviation (SD) for normally distributed variables and as median (IQR) for non-normally distributed variables. Categorical variables are presented as frequency (n) and percentage (%).

### **8.2 Between-Group Comparisons at Baseline**

Independent samples t-test was used for continuous variables and chi-square test for categorical variables to verify baseline comparability of the intervention and control groups.

### **8.3 Within-Group Pre-Post Comparisons**

Paired samples t-test was used to compare pre-test and post-test scores within each group (intervention and control) for all outcome variables.

### **8.4 Between-Group Comparisons of Change Scores**

Independent samples t-test was used to compare the magnitude of change (post-test minus pre-test) between the intervention and control groups for each outcome variable.

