### 2.2 Study Hypotheses

H1: Virtual reality application during foot care has an effect on pain level in individuals with diabetic foot ulcers.

H12: Virtual reality application during foot care has an effect on state anxiety in individuals with diabetic foot ulcers.

H13: Virtual reality application during foot care has an effect on vital signs in individuals with diabetic foot ulcers.

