#### **4.4 Sample Size**

The sample size was calculated using G\*Power 3.1 software. In the absence of studies specifically examining VR in diabetic foot patients, the effect size ( $d = 0.46$ ) was derived from a meta-analysis by Zeng et al. (2019) on VR effects on anxiety and pain. With  $\alpha = 0.05$  and power = 0.95, the required sample was 64 participants (32 per group). Accounting for approximately 5% possible attrition, 68 participants were randomized. Analyses were performed on the 64 participants who completed the study.

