## **5. RANDOMIZATION AND BLINDING**

### **5.1 Randomization**

Eligible participants were randomized to the intervention or control group using a computer-generated random selection method. Randomization was performed individually for each participant immediately after completion of pre-test measurements and prior to the onset of foot care. This approach minimized selection bias.

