### **7.3 Demographic Data**

A Demographic Information Form was used to collect participant characteristics including age, sex, education level, duration of diabetes, wound grade, and analgesic medication use.

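### The only between-group test uses raw change scores; adjusting for the pre-randomisation pre-test would usually be more precise and would remove the effect of chance baseline imbalance

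*Combined protocol and SAP*

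**What the plan says.** Section 8.4 gives the between-group analysis for each outcome: "Independent samples t-test was used to compare the magnitude of change (post-test minus pre-test) between the intervention and control groups". Section 8.3 adds paired t-tests within each group, and Section 8.5 adds Cohen's d. No ANCOVA, regression or other baseline-adjusted model appears anywhere in Section 8.

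The plan deals with baseline differences only in Section 8.2, where t-tests and chi-square tests are used "to verify baseline comparability of the intervention and control groups". It states no consequence if one of these tests is significant.

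Section 5.1 says each participant was randomised "immediately after completion of pre-test measurements and prior to the onset of foot care". Section 7.4 confirms that vital signs, STAI-I and VAS were all taken at that pre-test and repeated after foot care.

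Section 4.4 plans on d = 0.46 and alpha 0.05, with "power = 0.95, the required sample was 64 participants (32 per group"). It then says: "Accounting for approximately 5% possible attrition, 68 participants were randomized". The 64 completers were analysed. Section 4.4 does not say whether d is scaled to the post-test SD or the change-score SD, and no pre-post correlation is given.

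**The concern.** Subtracting the pre-test fixes its coefficient at 1. ANCOVA estimates that coefficient from the data. Under randomisation both methods target the same treatment effect, but the change score is the noisier of the two unless the true slope happens to be 1.

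A fixed coefficient also leaves the estimate dependent on the baseline difference that chance produced. When the slope is below 1, the group that starts higher tends to fall more through regression to the mean, and the change score counts that fall as effect. A baseline significance test neither measures nor removes this.

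Two things are at stake: precision in a trial of 64 analysed participants, and an estimate that a moderate chance imbalance can move by a noticeable part of the planned effect.

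**Working it through.** **Inputs from the documents.** 32 per group analysed, d = 0.46, alpha 0.05 (Section 4.4). Two-sided testing is assumed, because Section 2.2 words its hypotheses without direction ("Virtual reality application during foot care has an effect on pain level in individuals with diabetic foot ulcers").

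**Inputs assumed.** Pre-post correlation r = 0.3, 0.5, 0.7; equal pre-test and post-test SDs, relaxed in step 5; 0.46 expressed in post-test SDs. None of these is in the documents.

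**1. The plan's own figure.** A two-sided, two-sample t-test with d = 0.46 and power 0.95 needs 124 per group (103 one-sided), not 32. At 32 per group its power is 44% (57% one-sided). The stated 64 is therefore not reproduced for a between-group test. The attrition step is: 64 / 0.95 = 67.4, rounded up to 68. The sample-size mismatch is a separate matter; it is noted here because it sets the starting point for power.

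**2. Variance.** In units of the common variance:
- change score: 2(1 − r) = 1.40, 1.00, 0.60 at r = 0.3, 0.5, 0.7
- ANCOVA residual: 1 − r² = 0.91, 0.75, 0.51
- ratio: (1 + r)/2 = 0.65, 0.75, 0.85

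**3. Power at 32 per group for 0.46 post-test SD.** Noncentral t. Change score: standardised effect 0.46/√(2(1 − r)), 62 df. ANCOVA: 61 df, with residual variance inflated by 1 + 1/60 for the estimated slope.

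| r | Change score | ANCOVA |
|---|---|---|
| 0.3 | 33% | 47% |
| 0.5 | 44% | 55% |
| 0.7 | 65% | 71% |
| 0.8 | 82% | 85% |
| 0.9 | 98.2% | 98.5% |

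A simulation of 20,000 trials at each of r = 0.3, 0.5 and 0.7 agreed: 33%, 44%, 65% (32.9%, 44.2%, 64.5%) against 47%, 55%, 71%. Both estimators averaged 0.46.

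If 0.46 is instead in change-score SDs, change-score power is 44% at any r, and ANCOVA gives 61%, 55% and 50% at r = 0.3, 0.5 and 0.7.

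**4. Chance imbalance.** The SE of the baseline difference is √(2/32) = 0.25 SD. A gap of 0.3 SD or more in either direction has probability P(|Z| > 0.3/0.25 = 1.2) = 23%. The Section 8.2 t-test stays non-significant up to about 1.999 × 0.25 = 0.50 SD. Given a gap D, the change-score estimate shifts by −(1 − r)D. For D = 0.3 the size of the shift is 0.7 × 0.3 = 0.21, 0.5 × 0.3 = 0.15 and 0.3 × 0.3 = 0.09 SD. At r = 0.5 that is 0.15/0.46, about a third of the planned effect. In the simulation the change-score estimate correlated with the baseline difference at −0.58, −0.50 and −0.39; for ANCOVA the correlation was about zero.

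**5. Unequal SDs.** Change-score variance minus ANCOVA variance equals (SD_pre − r × SD_post)², which is never negative, so apart from ANCOVA's lost degree of freedom the direction holds for any SDs. The size does not. With SD_post/SD_pre = 1.25, in post-test SD units (SD_pre = 0.8):
- r = 0.5: variances 0.64 + 1 − 0.80 = 0.84 against 0.75; power 51% against about 55%. A gap of 0.3 pre-test SD shifts the estimate by (0.8 − 0.5) × 0.3 = 0.09 post-test SD.
- r = 0.7: variances 0.64 + 1 − 1.12 = 0.52 against 0.51; power 71% against 71%.

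**The case against.** The strongest reply is that nothing in Section 8.4 is invalid. A reader might infer from talk of regression to the mean that the planned test is biased. The documents do not support that: with randomisation after the pre-test, the change-score t-test is unbiased over repeated randomisations and keeps its type I error. The shift in step 4 is conditional on the baseline gap that occurred. This part of the reply stands in full.

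It also stands that the gain cannot be fixed from the documents. Section 7.4 has the same researcher re-measure eight outcomes with the same equipment around one procedure, so a high r is possible for some of them, and the gain would then be small. Equal SDs cannot be presumed either, because the post-test follows wound care in Wagner grade 3 or 4 ulcers. Nor do change scores always over-correct: they under-correct when r × SD_post exceeds SD_pre.

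A reader might also go further than the text allows in three ways. One is to say flatly that the trial has 44% power; that needs r = 0.5 with equal SDs, or d on the change-score SD, and Section 4.4 gives no scale. Another is to ask for wound grade and analgesic use as covariates because Section 7.3 lists "duration of diabetes, wound grade, and analgesic medication use". That section does not say when analgesic use was recorded, and no figure supports either covariate. The third is to treat the change as free. Section 3 gives a study period ending in June 2025 and Section 4.4 reports the analysis as done, so replacing the main test now would be a post hoc switch.

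The reply does not answer two points. No adjusted model is planned although the pre-test is a proper covariate for every outcome, and Section 8.2 offers no correction for imbalance.

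**Conclusion.** The point holds as one of efficiency and precision, not validity. At r between 0.3 and 0.7 with equal SDs, adjusting for the pre-test cuts the variance by 35% to 15% and adds roughly 14 to 6 points of power. It also removes a shift of 0.21 to 0.09 SD for a 0.3 SD baseline gap, a gap that arises in about 23% of trials this size. These sizes rest on an assumed r, equal SDs, two-sided testing and 0.46 on the post-test SD. The gain falls below 1 point near r = 0.9 and can be close to zero when the post-test SD is the larger.

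The improvement is worth making because it uses data already collected. It does not rescue the sample size: with equal SDs, 95% power at 32 per group would need r of about 0.87 even with ANCOVA.

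**What to change.** Add to Section 8.4, for each outcome, a linear model of the post-test on group and pre-test value. Report the adjusted mean difference with its 95% CI as the preferred estimate. State that this model was added after data collection, and report the planned change-score t-test beside it so that readers can see whether the conclusion depends on the choice. Wound grade and analgesic use need not be included.

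The cost is a small re-analysis of existing data in the SPSS version already named in Section 8, plus the post hoc label. The mismatch between sample size and power in Section 4.4 has to be dealt with separately.

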### **8.5 Effect Size**

Cohen's d was calculated to quantify the practical significance of between-group differences. Interpretation:  $d < 0.2$  = negligible;  $0.2-0.5$  = small;  $0.5-0.8$  = medium;  $> 0.8$  = large.

## 9. ETHICAL CONSIDERATIONS

The study was approved by the relevant institutional ethics committee and conducted in accordance with the Declaration of Helsinki. All participants received a full explanation of the study purpose, procedures, potential risks and benefits, and their right to withdraw at any time without consequence. Written informed consent was obtained from all participants prior to enrollment. No participant names or identifiable personal information are included in this document or in the reported dataset.

The investigators declare no conflicts of interest in relation to this study.

